6.2.17. Oropharyngeal Examination

Oropharyngeal examinations for clinical evidence of infection (i.e., Candida albicans) will be performed at each study visit as shown in the Time and Events Table. If there is evidence of infection, a culture swab may be taken and appropriate therapy should be instituted at the discretion of the Investigator. Subjects with culture-positive infection may continue in the study on appropriate anti-infective treatment at the discretion of the Investigator. The results of these assessments, and any relative pharmacotherapy, will be recorded in the subject's clinic notes and in the eCRF. After randomization, all culture positive results must be reported as adverse events.

6.2.18. Diary Card - Medical Problems/Medications Taken

Subjects will be instructed to record any medical problems they may have experienced and any medications used to treat those medical problems in their diaries from Screening (Visit 1) through the Follow-up Phone Contact.

Subjects will be instructed on how to complete the diary and will be asked to return completed diaries at each clinic visit. The study coordinator must review the diary at each clinic visit and will inquire about the diary data during the Follow-up Phone Contact as well. If the subject does not mention an event which is recorded on the diary, he/she should be questioned for further information in order to determine if there was the occurrence of an AE. Any confirmed AE and/or concurrent medication will be entered into the eCRF.

6.2.19. 12-lead ECG Assessment

A single 12-lead ECG and rhythm strip will be recorded prior to spirometry at the Screening Visit 1.

All ECG measurements will be performed with the subject resting in a supine position for approximately 5 minutes before each reading, which should be carried out after measurement of vital signs and before spirometry.

The investigator, a designated sub-investigator, or other appropriately trained site personnel, will be responsible for performing the 12-lead ECG recording on each study visit, if applicable. The investigator must provide his/her dated signature on the original paper tracing, attesting to the authenticity of the ECG machine interpretation.

6.2.20. Smoking Cessation Counselling

During the Screening Visit 1, 6, 10, and 14 or EW visit (if necessary), subjects will be given smoking cessation counselling, which includes advice regarding the following:

- the health effects that smoking may cause.
- the health benefits that may result if they stop smoking.
- if they do not feel capable of discontinuing smoking that their primary care physician may be able to discuss anti-smoking strategies with them.
- that they may discontinue smoking at any time during the study and will not have to be withdrawn from the study if they do so.

6.3. Pharmacogenetic Research

Information regarding pharmacogenetic research is included in Appendix 2. The IEC/IRB and, where required, the applicable regulatory agency must approve the PGx assessments before these can be conducted at the site. The approval(s) must be in writing and will clearly specify approval of the PGx assessments. In some cases, approval of the PGx assessments can occur after approval is obtained for the rest of the study. If so, then the written approval will clearly indicate approval of the PGx assessments is being deferred and the study, except for PGx assessments, can be initiated. When PGx assessments will not be approved, then the approval for the rest of the study will clearly indicate this and therefore, PGx assessments will not be conducted.

7. DATA MANAGEMENT

For this study subject data will be entered into GSK defined eCRFs, transmitted electronically to GSK and combined with data (e.g. laboratory data, diary data) provided from other sources in a validated data system.

Management of clinical data will be performed in accordance with applicable GSK standards and data cleaning procedures to ensure the integrity of the data, e.g., removing errors and inconsistencies in the data. Adverse events and concomitant medications terms will be coded using MedDRA and an internal validated medication dictionary, GSKDrug. An appropriate medical dictionary that covers all approved drugs in the region will be referenced. eCRFs (including queries and audit trails) will be retained by GSK, and copies will be sent to the investigator to maintain as the investigator copy. In all cases, subject initials will not be collected or transmitted to GSK according to GSK policy.

8. DATA ANALYSIS AND STATISTICAL CONSIDERATIONS

8.1. Hypotheses

The null hypothesis for the primary measure is that the change in BMD assessed at the total hip is worse for the FF/VI combination product arm compared with the VI arm. The alternative hypothesis that the change in BMD assessed at the total hip is not worse for the FF/VI arm compared with the VI arm.

This is also the null and alternative hypothesis for the secondary measure of BMD assessed at the L1-L4 lumbar spine.

8.2. Study Design Considerations

8.2.1. Sample Size Assumptions

This study will evaluate non-inferiority in both males and females separately as key secondary measures. 56 subjects per gender per treatment would provide 80% power to demonstrate non-inferiority by comparing the lower boundary of a two-sided 95% confidence interval on the treatment difference to -1%/year assuming a true treatment difference of -0.3%/year. In study SCO40041, approximately 20% of subjects did not provide post-baseline data, therefore 70 subjects per gender per treatment will be randomized (280 total subjects). Randomization will be stratified by gender.

For the primary evaluation of BMD for the total hip, males and females will be combined, and will have >90% power to demonstrate non-inferiority by comparing the lower boundary of a two-sided 95% confidence interval on the treatment difference to -1%/year assuming a true treatment difference of -0.3%/year.

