Another secondary objective is to evaluate the effect of FF on bone mineral density as assessed at the lumbar spine (L1-L4) by comparing FF/VI treatment with VI treatment in subjects with moderate COPD.

Study Design

This is a multi-center, randomized, double-blind, parallel-group study. The FF/VI inhalation powder once daily and VI inhalation powder once daily will be evaluated in subjects with COPD over 156 weeks. Subjects will sign the informed consent form (ICF) at Visit 0 and will be assigned a subject identifier. See Table 3 for further details. Subjects who meet all study inclusion and none of the exclusion criteria will begin a 14 to 21 day single-blind run-in period following Visit 1. Baseline BMD measurements will be collected between Visits 1 and 2. At Visit 2, eligible subjects will be randomized to double-blind study medication and entered into a 156-week treatment period. Randomisation will be stratified based upon gender. During the treatment period, clinic visits will occur every 3 months. BMD determined by dual-energy x-ray absorptiometry (DEXA) scans will be conducted every 6 months following randomization. A safety Follow-up Visit 15 will occur 7 days after the last treatment study day as a telephone contact. Subjects will be prescribed appropriate COPD therapy at the end of Treatment Visit 14 if required. There are no plans to provide the study drug for compassionate use following study completion.

The target enrolment across approximately 40 study centres is approximately 280 randomized subjects, to achieve approximately 224 who complete the 156-week treatment period. The total duration of subject participation will be approximately 159 to 160 weeks.

Study Endpoints/Assessments

Primary

• BMD measured at the total hip

Secondary

- BMD measurements by gender
- BMD measured at the lumbar spine (L1-L4)

Other

- Adverse Event reporting
- Serious Adverse Event reporting
- Incidence of fractures
- Incidence of pneumonias
- COPD exacerbations

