4. SUBJECT SELECTION AND WITHDRAWAL CRITERIA

4.1. Number of Subjects

Approximately 400 male and female subjects will be screened to randomize approximately 280 subjects, to obtain at least 224 who complete 156 weeks of treatment. Approximately 40 centres in multiple countries will be required to recruit for the study.

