11.3. Appendix 3: Country Specific Requirements

11.4. Appendix 4: Liver Chemistry Stopping and Followup Criteria

11.5. Appendix 5: Protocol Changes

This amendment applies to all study centers participating in HZC102972

Rationale

This protocol amendment is being implemented to revise and clarify exclusion criteria concerning participation in pulmonary rehabilitation programs; clarify the description of DEXA procedures and clinical labs; correction of typographical errors.

Section - Study Design

Original Text:

The target enrolment across approximately 40 study centres is approximately 400 randomized subjects, to achieve approximately 280 who complete the 156-week treatment period.

Amended Text:

The target enrolment across approximately 40 study centres is approximately 280 randomized subjects, to achieve approximately 224 who complete the 156-week treatment period.

Section 4.2. Inclusion Criteria - #6

Original Text:

Severity of Disease: Subject with a measured pre- and post-albuterol/salbutamol FEV_1/FVC ratio of < 0.70 at Screening (Visit 1).

Amended Text:

Severity of Disease: Subject with a measured post-albuterol/salbutamol FEV_1/FVC ratio of < 0.70 at Screening (Visit 1).

Section 4.3. Exclusion Criteria

Deleted Text (formerly criteria #23):

Pulmonary rehabilitation: Subjects who have participated in the acute phase of a Pulmonary Rehabilitation Program within 4 weeks prior to Screening Visit 1 or who will enter the acute phase of a Pulmonary Rehabilitation Program during the study. Subjects who are in the maintenance phase of a Pulmonary Rehabilitation Program are not excluded.

Section 4.4. Withdrawal Criteria – 3rd paragraph

Original Text:

Subject compliance with double-blind study medication will be assessed at Visits 2 through 14, by reviewing the dose counter on the NDPI.

Amended Text:

Subject compliance with double-blind study medication will be assessed from Visits 2 through 14, by reviewing the dose counter on the NDPI.

Section 6. Time and Events – Table 3

Original Text:

Collect Double-Blind Medication	Х	Х	Х	Х	Х	Х	Х	Х	Х	Х	Х	Х	Х	Х	
------------------------------------	---	---	---	---	---	---	---	---	---	---	---	---	---	---	--

Amended Text:

Collect albuterol (salbutamol) ¹⁴		Х	Х	Х	Х	Х	Х	Х	Х	Х	Х	Х	Х	Х	Х	
Dispense Single-Blind Medication	Х															
Collect Blinded Medication		Х	Х	Х	Х	Х	Х	Х	Х	Х	Х	Х	Х	Х	Х	

Section 6. Time and Events – Table 3 Footnotes

Original Text:

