# 9.3. Appendix 3: Assessment Windows

# 9.3.1. Definitions of Assessment Windows for Analyses: BMD Data

Analysis Set	Target	Analysis	Window	Analysis		
/ Domain		Beginning Timepoint	Ending Timepoint	Timepoint		
ITT", "Safety"	Week 26	Day 2	Day 272	VISIT 4		
ITT", "Safety"	Week 52	Day 273	Day 454	VISIT 6		
ITT", "Safety"	Week 78	Day 455	Day 636	VISIT 8		
ITT", "Safety"	Week 104	Day 637	Day 818	VISIT 10		
ITT", "Safety"	Week 130	Day 819	Day 1000	VISIT 12		
ITT", "Safety"	Week 156	Day 1001	Day 1182	VISIT 14		

In order to include all bone mineral density assessments, the analysis window has been increased to  $\pm$  3 months. A schematic of the above windowing is given below.

	273 454		637 818	-	1001 1182
Week 26 Visit 4	Week 52 Visit 6	Week 78 Visit 8	Week 104 Visit 10	Week 130 Visit 12	Week 156 Visit 14
2 272		455 636	-	819 1000	-

If there are multiple assessments within a window these will be averaged on the raw scale (i.e. before log transformation).

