# 9.4.2. Study Phases for Bone Mineral Density Measurements Taken at Visits (Bone Mineral Density Data Only)

Study Phase	Definition
Pre-Treatment	Date ≤ Study Treatment Start Date
On-Treatment	Study Treatment Start Date < Date ≤ Study Treatment Stop Date + 30 days (1 month)
Post-Treatment	Date > Study Treatment Stop Date + 30 days

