## 9.7. Appendix 7: Reporting Standards for Missing Data

## 9.7.1. Premature Withdrawals

Element	Reporting Detail	
General	
 
Subject study completion (i.e. as specified in the protocol) was defined as attendance at 13 post-randomisation visits over the schedule.
 
	
	Withdrawn subjects were not replaced in the study	
	Withdrawal visits will be slotted as per Appendix 3: Assessment Windows or will be summarised as withdrawal visits.	

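### Does it matter that 224 serves both as the number with post-baseline BMD data and as the number completing 156 weeks?

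*Protocol*

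**What the plan says.** Three places in the Protocol bear on the number.

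- **Section 8.2.1** sets 56 subjects per gender per treatment for 80% power in each gender, then inflates: "In study SCO40041, approximately 20% of subjects did not provide post-baseline data, therefore 70 subjects per gender per treatment will be randomized". It does not print 224, which follows from 4 × 56 or 280 × 0.80.
- **Section 4.1** says about 280 are randomised "to obtain at least 224 who complete 156 weeks of treatment".
- **The Summary (Study Design)** says "to achieve approximately 224 who complete the 156-week treatment period". Amendment 1 introduced this wording, as Appendix 5 shows.

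The SAP handles the two groups separately. Section 9.7.1 says that completion "was defined as attendance at 13 post-randomisation visits over the schedule". For subjects who stop early, the same section says "Withdrawal visits will be slotted as per Appendix 3: Assessment Windows or will be summarised as withdrawal visits". Section 9.3.1 opens the Week 26 BMD window on Day 2, and section 9.4.2 counts a BMD scan as on-treatment up to "Study Treatment Stop Date + 30 days (1 month"). Table 3 of the Protocol schedules a DEXA scan at Early Withdrawal.

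**The concern.** Having post-baseline data and completing three years are different conditions. Under the SAP's windows, a subject who leaves after a few months with one withdrawal scan can have post-baseline data, yet is not a completer. Completers are therefore a subset of subjects with a scan.

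If the 20% loss covers only subjects with no scan at all, 224 is the expected size of the larger group, and the expected number of completers should be smaller. Section 4.1 makes 224 a minimum for completers, which leaves no room for withdrawal after a first scan. That is hard to credit over three years in COPD.

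Two things could be at stake. The sample size might have been set on too small an allowance for loss, so that the stated power fails. Or a reader of the study report might judge retention against a figure that was never a completer forecast.

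**Working it through.** **Inputs.** Margin −1%/year, true difference −0.3%/year, two-sided 95% interval, 56 per gender per treatment and 20% loss (Protocol 8.2.1); SD 1.3%/year (SAP 2.5).

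**1. The inflation.** 56/0.80 = 70 per cell. 4 × 70 = 280 randomised. 280 × 0.80 = 224 = 4 × 56. No step is wrong.

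**2. The stated power.** With n per arm and δ the size of the true loss, power = Φ[(1.0 − δ)/(SD × √(2/n)) − 1.96].

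- By gender, n = 56: 0.7/(1.3 × √(2/56)) − 1.96 = 2.849 − 1.96 = 0.889, so power is 81.3% (80.6% by noncentral t). The Protocol claims 80%.
- Combined, n = 112: 0.7/(1.3 × √(2/112)) − 1.96 = 4.030 − 1.96 = 2.070, so power is 98.1%. The Protocol claims more than 90%.

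**3. The SAP's corrected table (Table 2), recomputed at 112 per arm.** Each cell shows computed / printed.

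| SD | −0.2%/yr | −0.3%/yr | −0.4%/yr |
|---|---|---|---|
| 1.3 | 99.6 / >99 | 98.1 / 98 | 93.2 / 93 |
| 1.4 | 99.0 / 99 | 96.3 / 96 | 89.4 / 89 |
| 1.5 | 97.9 / 98 | 93.7 / 94 | 84.9 / 85 |

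All nine cells agree. The power statements treat 224 as the number analysed, whatever 4.1 and the Summary call it.

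**4. How far the labels could drift apart.** Let x be the share of the 224 who have a scan and then withdraw. The documents give no value, so x is an assumption. Completers would be 224 × (1 − x). The last two columns put only those completers into the formula of step 2.

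| x | Completers | Power by gender, completers only | Combined power, completers only |
|---|---|---|---|
| 0% | 224 | 81.3% | 98.1% |
| 10% | 202 | 77.1% | 96.9% |
| 20% | 179 | 72.2% | 95.0% |
| 30% | 157 | 66.4% | 92.1% |

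These power columns describe an analysis that discarded every non-completer, which is not the planned one.

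**5. What the analysis uses.** SAP 7.1.4 excludes BMD data only after permanent discontinuation of study treatment, subject to the 30-day allowance in 9.4.2. SAP 7.1.5.1 fits a repeated-measures model to the BMD values by visit, without requiring completion. The windows in 9.3.1 were widened to keep scans in: "In order to include all bone mineral density assessments, the analysis window has been increased to" ± 3 months. A subject who withdraws after a scan contributes to the visits reached.

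**6. Where 224 is used as a rule.** Nowhere. Protocol 8.2.3 and 8.3.4 rule out sample size re-estimation and interim analysis. SAP 6.1.1 reports completion and withdrawal by arm without comparing them with a target.

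**The case for a change.** The strongest reply is that one of the passages must be imprecise under either reading, and that wording is cheap to correct. If the 20% is absence of any scan, 4.1 and the Summary overstate completers. If it is total three-year withdrawal in the earlier study, 8.2.1 describes it badly. Amendment 1 rewrote the Summary sentence and left the two unreconciled. In addition, the by-gender power has almost no slack (81.3% against 80%), so any information lost through partial follow-up could take it below the stated figure.

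The first part stands: the labels differ, and 4.1 and the Summary also differ between *at least* and *approximately*. But correcting the text requires knowing what the 20% counted in the earlier study, which the documents do not say. Restating 224 as subjects with a scan would also call for a separate completer forecast, resting on a withdrawal rate that the documents do not contain.

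The second part is fair as an observation about the secondary by-gender comparisons. It does not depend on the label, though. The loss of precision depends on when subjects leave and how the repeated scans correlate, neither of which is given, and renaming 224 would not alter it. If the 20% is total withdrawal, early leavers with scans add to the 56 per cell. The primary comparison stays above 90% even in the completers-only case with a 30% later loss.

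Nor is 224 a hard upper limit on completers. It comes from an approximate rate in another study applied to an approximate enrolment, so the actual count could fall on either side.

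**Conclusion.** No change is needed. Two labels are attached to one planning number, and they coincide only if no subject withdraws after a first scan. This is loose wording. The inflation, the enrolment figure and both power statements are correct as calculated, and all nine cells of the SAP's power table reproduce at 112 per arm.

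No figure that the trial relies on moves. Randomisation stays at 280, the power calculation still rests on 224 analysed, and the model takes all on-treatment scans whether or not the subject completes. A reader of the study report should take completion from the disposition table and treat 224 as an expectation. A single choice of term in 8.2.1, 4.1 and the Summary would be tidier, but nothing in the conduct, analysis or conclusions depends on it.

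This conclusion rests on the SAP's SD of 1.3%/year and on the on-treatment data rules in SAP 7.1.4 and 9.4.2 being applied as written.

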8.2.2. Sample Size Sensitivity

The following table presents the power of the study under different circumstances in terms of the standard deviation and the observed treatment difference in change from baseline in bone mineral density for the total hip.

	True Treatment Difference between FF/VI and VI								
SD	-0.2%/yr	-0.3%/yr	-0.4%/yr						
1.3%/yr	>99%	99%	96%						
1.4%/yr	>99%	98%	94%						
1.5%/yr	>99%	97%	91%						

8.2.3. Sample Size Re-estimation

No sample size re-estimation is planned for this study.

8.3. Data Analysis Considerations

8.3.1. Analysis Populations

All Subjects Enrolled Population: This population will consist of all subjects, for whom a record exists on the study database, including screen failures and any subject who was not screened but signed the informed consent form. This population will be used for reporting subject disposition, reasons for withdrawal prior to randomisation, and inclusion, exclusion and randomisation criteria deviations and SAEs for non-randomised subjects.

(Modified) Intent-to-Treat (ITT) Population: This population will consist of all subjects who are randomised and receive at least one dose of study drug. The ITT Population will be the primary population for all analyses of safety and efficacy measures.

8.3.2. Analysis Data Sets

The bone mineral density data will comprise the primary data set of interest. Details of derived data in analysis datasets to be created will be provided in the Reporting and Analysis Plan (RAP).

8.3.3. Treatment Comparisons

8.3.3.1. Primary Comparisons of Interest

BMD measured for the total hip will be summarized by visit and as change from baseline at each visit for raw values, percent changes from baseline, t-scores, and z-scores. The percent change from baseline in BMD for the total hip will be the primary endpoint, and analyzed using a repeated measures model with terms for treatment, time, time by treatment, baseline BMD, baseline BMI and gender. Contrasts will be formed using the time by treatment variable to provide 95% confidence intervals for the treatment difference with the unit of percent change per year. The 95% confidence interval will be compared to a lower bound of -1%/year in order to assess clinical non-inferiority. Any

additional covariates for the model, along with other details, including model inclusion and exclusion criteria for those covariates, will be determined a priori in a detailed Reporting and Analysis Plan (RAP) that will be completed prior to unblinding of the study.

The percent change from baseline in BMD at the L1-L4 region of the spine will also by summarized and analyzed in the same manner as the BMD data for the total hip.

8.3.4. Interim Analysis

No interim analysis is planned for this study.

8.3.5. Key Elements of Analysis Plan

8.3.5.1. Efficacy Analyses

No efficacy analyses are planned for this study

8.3.5.2. Safety Analyses

8.3.5.2.1. Extent of Exposure

The extent of exposure to study drug will be summarized by treatment group.

8.3.5.2.2. Adverse Events (AEs)

AEs will be coded using the standard GSK dictionary, Medical Dictionary for Regulatory Activities (MedDRA), and grouped by body system. AEs occurring pre-treatment, during active treatment and post-treatment will be summarized separately. The number and percentage of subjects experiencing at least one AE of any type, AEs within each body system and AEs within each preferred term will be presented for each treatment group. Separate summaries will be provided for all AEs, drug related AEs, SAEs, and for AEs leading to withdrawal.

8.3.5.2.3. Deaths and SAEs

All SAEs will be listed by treatment group. Deaths and SAEs will be documented in case narrative format.

8.3.5.2.4. Fractures

The number and percent of patients experiencing a bone fracture during the study will be summarized.

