6.2.5. Fractures

For any fractures that occur after the initiation of the double-blind study drug, the location of the fracture, and whether it is considered traumatic or non-traumatic must be recorded on the Fractures page of the eCRF. Severity of a fracture should be determined by the Investigator. Details regarding the information to be captured for fractures will be provided in the SPM.

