6.2.6. COPD Exacerbations and Pneumonias

For the purpose of this study, exacerbation of COPD is defined by a worsening of symptoms requiring additional treatment as follows:

- A mild COPD exacerbation: managed by subject with increased use of prn medications
- A moderate COPD exacerbation: requires treatment with antibiotics and/or systemic corticosteroids
- A severe COPD exacerbation: requires hospitalization

Any subject experiencing worsening of symptoms should:

- Contact his/her study investigator and/or research coordinator immediately, and report to the study clinic as required
- If the subject is unable to contact his/her study investigator and/or research coordinator, they should contact their primary care physician (or other health care practitioner as required) and contact their study site as soon as possible
- If the subject seeks emergent/acute care for worsening respiratory symptoms, he/she should inform the caring Health Care Provider (HCP) to contact the investigator as soon as possible.

Subjects with presence of worsening respiratory symptoms will be classified by the Investigator as having:

• A mild/moderate/severe COPD exacerbation and/or pneumonia

OR

- A lower respiratory tract infection (LRTI) [i.e. other than pneumonia]
- Background variability of COPD
- A non-respiratory related disease
- Other respiratory related disease

The time period for collection of COPD exacerbations will begin from the time of Visit 2 (Randomization) and will end when the 7 ± 2 day Follow-up period has been completed.

COPD exacerbations should not be recorded as an adverse event, unless they meet the definition of a Serious Adverse Event. For the purposes of this study, COPD exacerbations will be collected and recorded on the exacerbation log in the eCRF. Exacerbations that meet the definition of an SAE, will be recorded on the appropriate eCRF section and should be reported to GSK for all subjects regardless of whether or not they are randomized to blinded study medication.

Subjects are excluded from participating if any of the following apply:

- They have poorly controlled COPD, defined as the occurrence of the following in the 12 weeks prior to Screening Visit 1: Acute worsening of COPD that is managed by the subject with corticosteroids or antibiotics or that requires treatment prescribed by a physician or requires hospitalization.

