#### 7.5. On-treatment Fractures

Fracture events including the number and percentage of subjects recorded as having at least one bone fracture, location of fractures and whether they were traumatic or not traumatic (severity) will be summarised. If a subject suffers fractures in multiple locations with the same date of fracture, this is considered to be one fracture incident. The frequency and percentage of subjects with 0, 1, 2 and more than 2 fracture incidents will also be summarised.

In addition, the rates of fractures will be summarised as described in Section 9.6.3. The details of the planned displays are in Appendix 12: List of Data Displays.

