# 9.4.3. Study Phases for Adverse Events and All Other Data Recorded in Logs (excluding Concomitant Medications)

Study Phase	Definition
Pre-Treatment	Event Onset Date < Study Treatment Start Date
On-Treatment	Study Treatment Start Date ≤ Event Onset Date ≤ Study Treatment Stop Date + 1
Post-Treatment	Event Onset Date > Study Treatment Stop Date + 1

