2.18.	SAF	SAFE_T04	Analysis of On-treatment Percentage Change from Baseline in Bone Mineral Density (g/cm^2) at the Lumbar Spine by Gender		SAC [1]	
2.19.	SAF	SAFE_T05	On-treatment Bone Mineral Density (g/cm^2) at the Lumbar Spine Mixed Model Repeated Measures Analysis Interaction Test	Only include the interaction for gender	SAC [1]	

Safety:	Tables				
No.	Population	IDSL / Example Shell	Title	Programming Notes	Deliverable [Priority]
Vital Si	gns, Incidence	of Fracture, Pneu	monia, X-rays and COPD Exacerbations		
2.20.	SAF	VS1	Summary of Vital Signs	All variables to have a row for minimum and maximum ontreatment values along with having a row for early withdrawal.	SAC [1]
2.21.	SAF	VS1	Summary of Change from Baseline in Vital Signs	All variables to have a row for minimum and maximum ontreatment values along with having a row for early withdrawal.	SAC [1]
2.22.	SAF	SAFE_T07	Summary of On-treatment Pneumonia		SAC [1]
2.23.	SAF	SAFE_T08	Summary of On-treatment Fractures		SAC [1]
2.24.	SAF	SAFE_T09	Summary of On-treatment Moderate/Severe COPD Exacerbations		SAC [1]
2.25.	SAF	SAFE_T09	Summary of On-treatment Severe COPD Exacerbations		SAC [1]
Spiron	netry				
2.26.	SAF	SAFE_T10	Summary of On-treatment FEV 1 (L) at Clinic Visits		SAC [1]
2.27.	SAF	SAFE_T10	Summary of On-treatment FVC (L) at Clinic Visits		SAC [1]
Advers	e Events			·	
2.28.	SAF		Overview of On-treatment Adverse Events During the Study		SAC [1]
2.29.	SAF	AE1	Summary of On-treatment Adverse Events Leading to Permanent Discontinuation of Study Treatment or Withdrawal from the Study by System Organ Class and Preferred Term	IDSL - Include rates.	SAC [1]

Safety:	Safety: Tables					
No.	Population	IDSL / Example Shell	Title	Programming Notes	Deliverable [Priority]	
2.30.	SAF	AE1	Summary of On-treatment Adverse Events by System Organ Class and Preferred Term	ICH E3. Include rates.	SAC [1]	
2.31.	SAF	AE1	Summary of On-treatment Adverse Events by Age	IDSL. Use age ranges: 40 to ≤ 65, >65 to ≤ 74, and ≥75	SAC [1]	
2.32.	SAF	AE1	Summary of On-treatment Adverse Events by Region	IDSL, North America vs Europe	SAC [1]	
2.33.	SAF	AE1	Summary of On-treatment Adverse Events by Gender	IDSL	SAC [1]	
2.34.	SAF	AE1	Summary of On-treatment Adverse Events by Smoking Status	IDSL	SAC [1]	
2.35.	SAF	AE1	Summary of Post-treatment Adverse Events by System Organ Class and Preferred Term	ICH E3. Include rates.	SAC [1]	

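### The protocol's summary of fractures during the study becomes on-treatment only in the SAP, and the narrowing is not declared

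*Protocol*

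**What the plan says.** The protocol sets a study-wide scope for fractures. Section 8.3.5.2.4 reads: "The number and percent of patients experiencing a bone fracture during the study will be summarized". Collection is equally broad in section 6.2.5, which begins "For any fractures that occur after the initiation of the double-blind study drug" and gives no end date tied to the last dose. By contrast, Protocol 8.3.5.2.2 divides adverse events into pre-treatment, active-treatment and post-treatment periods. Fractures get no such division. SAP 2.2 carries the endpoint forward as fracture incidence, also without a treatment limit.

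The analysis sections of the SAP are narrower. Section 7.5 is headed as on-treatment. Its text begins "Fracture events including the number and percentage of subjects recorded as having at least one bone fracture" and gives no window of its own. The only dedicated fracture display among the safety tables in SAP 9.9.6 is Table 2.23, "Summary of On-treatment Fractures". For adverse events and other log data, SAP 9.4.3 defines on-treatment as "Study Treatment Start Date ≤ Event Onset Date ≤ Study Treatment Stop Date + 1". SAP 9.4.2 has a separate rule for BMD scans, which run to 30 days after treatment stops.

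SAP Table 1 has three rows of changes from the protocol's analysis: the model, the analysis population and the power table. None concerns fractures.

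**The concern.** Fracture is the clinical harm behind the BMD endpoint. Protocol 3.2 justifies the total hip as the primary site by the consequences of hip fracture. In a trial built around bone safety, a reader of the report will expect the fracture count to be the one the protocol describes. Under the SAP, a subject whose only fracture occurs two or more days after the last dose is counted as having none in Table 2.23, although the protocol collected the event and said it would be summarised. Because Table 1 is silent, nothing tells the reader that the scope has changed.

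At stake is the completeness of a descriptive safety count and its traceability to the protocol. No hypothesis test depends on it.

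**Working it through.** The documents give no expected fracture count or rate, so there is no stated figure to reproduce. The check is a comparison of text followed by a sizing of the gap.

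**Does the SAP deliver the protocol's summary elsewhere?**

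- Tables 2.47 and 2.48 (adverse events of special interest) include a group for low BMD and associated fractures, but both are on-treatment only. They do not restore the count.
- Table 2.35 shows post-treatment adverse events by preferred term. A late fracture reported as an adverse event appears there, spread over whichever terms are used, with no fracture total.
- Table 2.42 (serious adverse events) has no on-treatment limit in its title, so a serious late fracture appears there.
- Listing 30 shows every fracture with a column for study phase.

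No table gives the number and percent of subjects with a fracture over the whole study.

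**How much time is left out for a subject dosed up to the last visit?**

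- Inputs: follow-up contact at Visit 14 or Early Withdrawal + 7±2 days (Protocol Table 3), adverse event collection to that contact (Protocol 6.2.8), on-treatment window ending at stop + 1 day (SAP 9.4.3), 280 randomised subjects (Protocol 8.2.1) and 156 weeks = 1,092 days of treatment.
- Assumptions: the last dose falls on the visit day, and fractures are collected to the same contact as adverse events.
- Days omitted = follow-up day − 1 = 5 − 1, 7 − 1 or 9 − 1 = 4, 6 or 8.
- Nominal person-years = 280 × 6 / 365.25 = 4.6. The range is 280 × 4 / 365.25 = 3.1 to 280 × 8 / 365.25 = 6.1.
- For comparison, on-treatment time if all 280 complete = 280 × 1,092 / 365.25 = 837 person-years.
- Fractures omitted at an assumed 2 to 5 per 100 person-years = 4.6 × 0.02 to 4.6 × 0.05 = 0.09 to 0.23.
- With an assumed 1 to 5 per 100 and the full 4 to 8 days, the range is 3.1 × 0.01 = 0.03 to 6.1 × 0.05 = 0.31.

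**What if the last visit comes after the last dose, or subjects stay in the study off drug?**

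- If the last visit falls 30 days after the last dose (assumption), the days omitted for that subject are 30 + 5 − 1 = 34 to 30 + 9 − 1 = 38.
- Protocol 4.4 leaves participation after premature discontinuation to discussion with the sponsor or site monitor. Protocol 6.2.7 stops drug at once for liver criteria but withdraws the subject only after liver monitoring. SAP 7.1.4 has a rule for BMD data collected after permanent discontinuation. Off-drug time in the study is therefore possible, but no document says how much to expect.
- Illustration: if 10% of 280 = 28 subjects stayed a mean of 1 year off drug, 28 person-years would be omitted, or 28 × 0.02 to 28 × 0.05 = 0.6 to 1.4 fractures.
- Wider illustration: 14 to 56 subjects (5% to 20%) for 0.5 to 1.5 years gives 7 to 84 person-years. At 1 to 5 per 100 that is 0.07 to 4.2 fractures.

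**Exacerbations, as a side check.** Protocol 6.2.6 collects them for a period that "will end when the 7 ± 2 day Follow-up period has been completed". Tables 2.24 and 2.25 are on-treatment. Non-serious exacerbations are not recorded as adverse events, so a non-serious moderate event in follow-up reaches no summary table. It would appear only in Listing 28. Severe exacerbations require hospitalisation, which makes them serious, so they reach the serious adverse event tables.

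**The case against.** The strongest reply is that little is lost. Late fractures remain in Listing 30, and under the protocol's broad adverse event definition they should also reach Table 2.35, and Table 2.42 if serious. SAP 7.1.4 gives a reason to set aside BMD data after permanent discontinuation, namely that inhaled therapy may then be switched, and the same reasoning could support an on-treatment fracture count. All of this stands. It shows that the events stay in the report and that an on-treatment count is legitimate. It does not supply the study-wide count that the protocol describes, and SAP 7.1.4 does not mention fractures.

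A second reply is that the one-day cut is inferred. That is correct: it rests on treating the Fractures eCRF page as log data under SAP 9.4.3. The on-treatment restriction itself is explicit in the heading of 7.5 and in the title of Table 2.23, whatever the exact cut.

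A reader might infer more than the documents support:

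- **That the 30-day BMD window and the one-day fracture window conflict.** Scans are tied to visits, whereas a fracture has its own onset date. SAP 9.4 sets phase rules by type of data, and different windows are a defensible choice.
- **That the cut favours a finding of not worse.** Non-inferiority is tested on BMD alone, and fractures are descriptive. Removing late events can lower the total, but nothing shows that it lowers one arm more than the other. SAP 9.4 also counts events with missing dates as on-treatment in treated subjects unless there is evidence otherwise, which works the other way.
- **That exacerbations show the same mismatch.** Protocol 8.3.5.2.5 does not say that the exacerbation summary covers the whole study, so an on-treatment table contradicts nothing there.

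**Conclusion.** The point holds as a mismatch between protocol and SAP. The protocol describes a study-wide count and percentage of subjects with a fracture, the SAP plans an on-treatment one, and Table 1 does not record the change. The consequence is small: about 0.1 to 0.2 fractures across the trial if all 280 subjects are dosed to the last visit, at an assumed 2 to 5 per 100 person-years. It could exceed one event only if a material share of subjects stay in the study off drug, which the protocol permits but does not quantify. The fracture rates and the off-drug scenarios are assumptions, not figures from the documents. The direction of any effect on the comparison between arms is unknown, and the primary BMD analysis is untouched. The change is worth making because the outcome is the one the trial is about and the cost is close to nil.

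**What to change.** In SAP 7.5 and Table 2.23, report the number and percent of subjects with a fracture from first dose to the end of study follow-up, with separate on-treatment and post-treatment rows beneath. Keep the rate per 100 treatment-years on the on-treatment row, where numerator and exposure match. State the window in 7.5 so that it need not be inferred from 9.4.3. If the sponsor prefers to keep the on-treatment restriction, the minimum is to record and justify it in SAP Table 1.

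Optionally, add a post-treatment row for moderate or severe exacerbations to Table 2.24, since non-serious moderate events in follow-up are otherwise not summarised. Table 2.25 needs no change.

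The cost is a few words in the SAP and one or two rows in existing tables. Listing 30 already calls for fractures by study phase, so no new data collection is needed.
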